1.3 Rationale

The aim of the study is to assess the effects of the JAK1 inhibitor Itacitinib as a second line treatment on patients with advanced inflammatory HCC. Inflammatory cells have been seen to produce cytokines that can activate STAT3 via the JAK pathway. This in turn enables them to become transcription factors and drive the expression of multiple genes important for cell activation, localisation, survival, and proliferation. It is therefore hypothesised that the ability of Itacitinib to inhibit the JAK pathway may cause a positive response in the patient's tumour.

1.4 Risk / Benefit Assessment

1.4.1 Potential Benefits

Patients may not directly benefit from enrolment on this trial, however, pre-clinical data has confirmed the ability of ITACITINIB in the Inhibition of JAK signalling and therefore may be therapeutic for the treatment of diseases such as MF, RA, psoriasis, GVHD, solid tumours, and B-cell malignancies, as JAKs serve to transduce extracellular signals from a number of cytokines and growth factors that are upregulated and thought to be involved in the pathogenesis of such conditions.

1.4.2 Potential Risks and their Management

Itacitinib affects the immune system. Therefore, subjects must be monitored closely and administration should be discontinued if there is evidence of clinically significant infection or cancer progression. For this population monitoring and treatment of elevated liver function values a hyperlipidaemia will be tailored as appropriate to the individual subject characteristics; cholesterol-lowering agents, such as 3-hydroxy-3-methyl-glutaryl-coenzyme A reductase inhibitors, should be used with caution, as these drugs are also associated with liver function abnormalities. The study is being reviewed by a steering committee.

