4.2 Dose Modifications

4.2.1 Dose Interruptions

Clinically indicated dose interruptions of JAK-I are permitted for up to 14 days. If a treatment break continues for greater than 14 days the patient will need to withdraw from study.

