4.2.2 Dose Reductions

Toxicities will be graded according to NCI-CTCAE version 4.03. Dose reductions are to be made according to the system showing the greatest degree of toxicity.

All patients will receive 400mg QD until the patient suffers from disease progression. Should any patients suffer from significant toxicity the dose can be reduced to 300mg QD.

| Toxicity | Grade 1 | Grade 2 | Grade 3 | Grade 4 |
|--------------------|---------------------------------|---------------------------------|---|---|
| Non-haematological | Continue at the same dose level | Continue at the same dose level | Withhold dose until toxicity is grade ≤ 1 , then resume treatment at the same dose level. If the patient experiences a second grade 3 toxicity, withhold dose until the toxicity is grade ≤ 1 , then reduce dose to 300mg QD and resume treatment. If there is no toxicity grade ≥ 1 after 28 days re-escalation to 400mg QD should be done for 28 days. Without further | Withhold dose until toxicity is grade ≤ 1 , resume treatment at reduced dose level of 300mg QD or discontinue at the discretion of the principal investigator. |

| | | | | |
|----------------|---------------------------------|---------------------------------|---|---|
| | | | aggravation of toxicity full dose can be continued. Generally the dose with toxicity grade ≤ 1 should be maintained. | |
| Haematological | Continue at the same dose level | Continue at the same dose level | Withhold dose until toxicity is grade ≤ 1 , then resume treatment at the same dose level. If the patient experiences a second grade 3 toxicity, withhold dose until the toxicity is grade ≤ 1 , then reduce dose to 300mg QD and resume treatment. If there is no toxicity grade ≥ 1 after 28 days re-escalation to 400mg QD should be done for 28 days. Without further aggravation of toxicity full dose can be continued. Generally the dose with toxicity grade ≤ 1 should be maintained. | Withhold dose until toxicity is grade ≤ 1 , resume treatment at reduced dose level of 300mg QD or discontinue at the discretion of the principal investigator. |

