4.2.3 Study Withdrawal

A subject **must** be withdrawn from **study treatment** IF:

- The subject has experienced an unacceptable toxicity
- The subject is unwilling to continue receiving study treatment.
- The subject has experienced clinical deterioration/disease progression.
- In the opinion of the investigator, it is in the best interest of the subject not to continue receiving the study treatment.
- The subject becomes pregnant.
- Consent to receive treatment is withdrawn.
- Termination of the study by the sponsor.
- Termination of the study by the local health authority, IRB, or IEC.

A subject **may** be withdrawn from **study treatment** if, during the course of the study:

- Is found not to have met eligibility criteria; the subject would be withdrawn if the investigator, determines that the subject would not benefit from participation in the study due to the eligibility deviation.
- Is noncompliant with study procedures or study drug administration in the opinion of the investigator.

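### Section 1.4.2 stops itacitinib for clinically significant infection, but the dose table in 4.2.2 resumes 400 mg after a first grade 3 event, and nothing says which governs

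*Combined protocol and SAP*

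**What the plan says.** Section 1.4.2 (Potential Risks and their Management) starts from the drug's effect on the immune system and gives a dosing instruction: "administration should be discontinued if there is evidence of clinically significant infection or cancer progression". No grade, type or duration of infection is attached, and nothing says whether the drug may later be restarted.

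The dosing rules are in section 4.2:

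- **4.2.1** allows clinically indicated interruptions of up to 14 days, and then: "If a treatment break continues for greater than 14 days the patient will need to withdraw from study".
- **4.2.2** sets the general rule, "All patients will receive 400mg QD until the patient suffers from disease progression", with a reduction to 300 mg for significant toxicity. Its table is by CTCAE grade and has two rows, non-haematological and haematological. For grades 1 and 2 it says "Continue at the same dose level". For a first grade 3 event the dose is withheld until grade 1 or less, "then resume treatment at the same dose level". For grade 4 it is withheld until grade 1 or less, and the site may "resume treatment at reduced dose level of 300mg QD or discontinue at the discretion of the principal investigator".
- **4.2.3** lists reasons for mandatory withdrawal from treatment. They include "The subject has experienced an unacceptable toxicity", "The subject has experienced clinical deterioration/disease progression" and the investigator's opinion that stopping is in the patient's best interest. Infection is not named.

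In sections 3 and 4, infection appears only as an entry exclusion (3.3.2).

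**The concern.** For the same serious infection, one part of the protocol says to discontinue and another says to resume. Neither refers to the other and no order of precedence is given. Someone deciding a dose will probably turn to the table in 4.2.2 rather than to the risk narrative in section 1.

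This is a patient-safety matter. Section 1.2.3 warns that infections may increase with itacitinib whether it is given alone or in combination, and asks for strict monitoring. A site that works from the table can return a patient to full dose after an infection for which 1.4.2 says to discontinue. A site that works from 1.4.2 would stop. Safety and tolerability is a primary objective (2.1), so the descriptive summary of adverse events by their effect on study drug (7.2.1) would partly reflect which section each site followed.

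**Working it through.** The plan gives no figure on this point, so the check is a comparison of texts. It treats infection as a non-haematological toxicity, since the table has only the two rows.

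**Step 1. What 'discontinued' means.** Section 1.4.2 does not say whether the stop is permanent. Two features favour a stop. One verb covers both infection and cancer progression, and progression is a mandatory reason for ending treatment in 4.2.3. The grade 4 cell of 4.2.2 also sets discontinuing against resuming. Neither feature is conclusive, so both readings are carried forward.

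**Step 2. Each grade against 1.4.2.**

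| Grade | Table in 4.2.2 | If 1.4.2 means a stop | If 1.4.2 means a hold |
|---|---|---|---|
| 1 | Continue | No conflict unless judged clinically significant, which is unlikely | Same |
| 2 | Continue | Conflict only if judged clinically significant | Conflict only if judged clinically significant |
| 3, first event | Withhold to grade 1 or less, resume 400 mg | Conflict if it settles within 14 days | No conflict |
| 4 | Withhold to grade 1 or less, then 300 mg or discontinue | No contradiction: discontinuing satisfies both, but a restart is allowed | No conflict |

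The grade 3 and 4 entries assume that an infection of that grade counts as clinically significant.

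**Step 3. The 14-day limit.** If a grade 3 infection takes more than 14 days to settle, 4.2.1 requires withdrawal and agrees with 1.4.2 read as a stop. The conflict is therefore confined to infections that settle to grade 1 or less within 14 days. A second grade 3 event also resumes, at 300 mg, so the same issue recurs at the lower dose.

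**Step 4. How often it could arise.** Section 1.2.3 reports serious pneumonia in 3 and serious urinary tract infection in 2 myelofibrosis patients on monotherapy. That is 3 + 2 = 5 reports, possibly in overlapping patients. No denominator, grade, duration or dosing action is given. These reports show that serious infection occurs on the drug, but they give no rate for the planned 25 patients.

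**Step 5. Effect on the design.** The two-stage rule in 7.1 is stated in responses: stop if 0 of 15, success if at least 4 of 25. None of its inputs involves infection or the dosing rule, so the sample size and error rates stand.

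**The case against.** The strongest reply is that 1.4.2 is itself part of the protocol, is specific to infection, and should prevail over a generic table. A site that resumes dosing against it is not following it. There are also several ways to stop. Unacceptable toxicity and best interest are both on the mandatory list in 4.2.3. A serious infection might count as clinical deterioration. Section 3.5 allows stopping on the investigator's decision, and 8.3 leaves the clinician free to depart from protocol treatment in the participant's interest. Finally, 'discontinued' may mean only a temporary stop.

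Much of this stands. The specific-over-generic reading is reasonable, but the protocol does not state it. The withdrawal items bind only once an investigator has made the judgement, and unacceptable toxicity is undefined. If a hold was meant, the grade 3 conflict disappears; the text leaves this open. The investigator brochure may say more but is not available here.

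Two stronger readings are tempting, and the documents support neither.

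- *A reader might infer that the table contradicts 1.4.2 at every grade from 2 upwards.* Grade 2 conflicts only if a grade 2 infection is judged clinically significant, and grade 4 expressly allows discontinuation.
- *A reader might infer neglect because progression is named as a stop reason in several sections and infection in none.* Progression is an efficacy event and has to be named separately. An infection on treatment is an adverse event and can come under unacceptable toxicity. No other specific toxicity is named in the stop lists either.

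The haematology sentence in 1.2.3 that mentions both interruption and discontinuation does not settle the meaning in 1.4.2, because it is not about infection.

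**Conclusion.** The point holds in a limited form. There is one firm conflict: 4.2.2 resumes 400 mg after a first grade 3 event, while 1.4.2 says to discontinue. It rests on three assumptions: a grade 3 infection is clinically significant, 'discontinued' means a stop, and the infection settles to grade 1 or less within 14 days. Grade 4 is latitude rather than contradiction, and grade 2 is conditional on judgement.

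The exposed patient is one whose site follows the table cell and makes no separate judgement under 4.2.3. How many of the 25 that might be cannot be estimated from the documents. The other safeguards (exclusion of serious active infection at entry, monitoring, SAE reporting within 24 hours, a steering committee every 6 months) prevent, detect or report infection. None of them sets the dose.

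This should be corrected because it concerns safety on an immunosuppressive drug and is cheap to resolve. It does not call the endpoints, sample size or error rates into question.

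**What to change.** The sponsor should first decide whether 1.4.2 means a stop or a hold, since that decides whether a conflict exists.

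- **If a stop:** add clinically significant infection to the mandatory list in 4.2.3, and add a line in 4.2.2 that this overrides the grade 3 and grade 4 resume cells.
- **If a hold:** change the infection wording in 1.4.2 from discontinued to withheld until resolved, so that it matches 4.2.1 and 4.2.2, including the 14-day limit.

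In either case, define the term once and refer to it from each section. A workable definition is an infection of CTCAE grade 3 or higher, or one needing intravenous treatment or hospitalisation. That threshold is a proposal and has no source in the documents; the sponsor may prefer another. If the intravenous or hospitalisation criterion is kept, the new line in 4.2.2 should also override the grade 2 continue cell for infections that meet it.

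The cost is a wording amendment, with no extra patients or data. The downside is a few more dose holds or discontinuations.

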2 OBJECTIVES AND ENDPOINTS

2.1 Primary Objective and Endpoint

| Objective | Endpoint |
|--|---|
| To assess the safety and tolerability of Itacitinib in patients with advanced hepatocellular carcinoma (HCC) | As assessed by adverse events according to the Common Terminology Criteria for Adverse Events (CTCAE) version 4.03. |
| To assess the efficacy of Itacitinib by overall response rate (ORR) | ORR defined as complete response, partial response, stable disease or progressive disease at 8 weeks post treatment according to modified RECIST criteria (mRECIST) version 1.1 |

2.2 Secondary Objectives and Endpoints

| Objective | Endpoint |
|---|--|
| To assess the efficacy of Itacitinib by progression free survival (PFS) | PFS, defined as time from study entry to first evidence of disease progression assessed by mRECIST v1.1 or death due to any cause. |
| To assess the efficacy of Itacitinib by overall survival (OS) | OS, defined as time from study entry to death due to any cause. |

2.3 Translational / Exploratory Objectives and Endpoints

| Objective | Endpoint |
|--|---|
| 1. To assess for presence of predefined JAK1 mutations in tumour tissue and correlate with treatment outcome | To assess for presence of predefined JAK1 mutations in tumour tissue (NGS) and correlate with treatment outcome (mRECIST) |
| 1. To assess for presence of predefined JAK1 mutations in ctDNA | To assess for presence of predefined JAK1 mutations in ctDNA (NGS) |
| 1. To correlate changes in pro-inflammatory cytokines with treatment response | To correlate changes in pro-inflammatory cytokines (multiplex cytokine bead array) with treatment response (mRECIST) |

[figure not shown]
3 STUDY DESCRIPTION

[figure not shown]
3.1 Design

This is a single arm phase Ib study to evaluate the effect of Itacitinib (a JAK1 inhibitor) in ~25 patients with advanced HCC. Eligible patients will receive Itacitinib every 400mg QD until disease progression, unacceptable toxicities or withdrawal of consent.

The first 10 patients will undergo attenuated pharmacokinetic profiling in cycle 1.

3.2 Study Flowchart

3.3 Study Population

3.3.1 Inclusion Criteria

Patients who meet all of the following inclusion criteria will be considered eligible for this study:

1. Aged 18 or over
2. Diagnosis of hepatocellular carcinoma. If primary diagnosis of HCC: diagnosis based on the following criteria:
 - cyto-histological criteria, OR
 - radiological criteria: Focal lesion >1 cm with arterial hypervascularization in 2 coincident imaging techniques (CT, MRI, or US), OR
 - combined criteria: one imaging technique showing a focal lesion 1-2 cm with arterial hypervascularization AND AFP levels >400 ng/mL, OR
 - combined criteria: one imaging technique showing a focal lesion >2 cm with arterial hypervascularization AND AFP levels >200 ng/mL
3. Progression or intolerance to first line therapy if child-Pugh A and B up to 7 points (in patients receiving anticoagulant therapy; Child-Pugh score up to 5 points; INR category not regarded for calculation of the Child-Pugh score)– N.B: Date of patients last dose of therapy must be more than 28 days before enrolment into this study
4. Child-Pugh B7 in patients who are treatment naive
5. ECOG Performance status 0, 1 or 2.
6. Adequate organ function as defined by:
 - Adequate hematologic function (ANC $\geq 1.0 \times 10^9/l$, platelet count $\geq 50 \times 10^9/l$, and hemoglobin $\geq 9g/dl$).
 - Serum creatinine concentration < 1.5 times the upper limit of normal (ULN) and/or creatinine clearance >60 ml/min
 - Bilirubin level < 1.5 X ULN
 - PT-INR/PTT < 1.5 x ULN
7. For women of child-bearing potential (defined as women who have not undergone surgical sterilization with a hysterectomy, and/or bilateral oophorectomy, and are not postmenopausal, defined as ≥ 12 months of amenorrhea) must have a negative serum pregnancy test within 14 days prior to the first study drug administration

Effective contraception must be used throughout the duration of the study and up to 30 days following

the last dose of the investigational medicinal product (IMP). Effective forms of contraception include complete abstinence from sexual intercourse, double barrier methods (condom with spermicide in conjunction with use of an intrauterine device or condom with spermicide in conjunction with use of a diaphragm), birth control patch or vaginal ring, oral, injectable, or implanted contraceptives and surgical sterilization (tubal ligation or vasectomy). Sperm and ova donation are prohibited during the duration of the study and 30 days after the last dose. 8. Written informed consent prior to initiation of any study procedures and willing and able to comply with the study schedule

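### Eligibility does not require a lesion measurable by mRECIST although the design counts responses; criteria 3 and 4 and the stated aim also need reconciling

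*Combined protocol and SAP*

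**What the plan says.** All references are to the combined protocol and SAP.

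**Combining rule.** Section 3.3.1 states: "Patients who meet all of the following inclusion criteria will be considered eligible for this study".

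**Lesions.** The only lesion wording in section 3.3.1 is in criterion 2, which lists four alternative routes to a diagnosis of HCC. One is "radiological criteria: Focal lesion >1 cm with arterial hypervascularization in 2 coincident imaging techniques (CT, MRI, or US), OR". Two others combine one imaging technique with an AFP threshold. The remaining route is simply "cyto-histological criteria, OR", with no lesion attached. Section 3.3.2 (exclusions) does not mention measurable disease. Table 1 in section 3.4.1 schedules a tumour assessment at screening but sets no condition on what it must show.

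**Endpoint and analysis.** Section 2.1 makes ORR by mRECIST at 8 weeks a primary endpoint. Section 7.1 stops the trial at 0 responses in the first 15 patients and declares success at 4 or more in 25. Section 7.2.1 analyses efficacy by intention to treat. It counts a patient as evaluable with a week-8 tumour assessment, or with progression or death before then.

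**Prior therapy.** Criterion 3 reads "Progression or intolerance to first line therapy if child-Pugh A and B up to 7 points". Criterion 4 reads "Child-Pugh B7 in patients who are treatment naive".

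**Population.** Section 1.3 describes itacitinib "as a second line treatment on patients with advanced inflammatory HCC". Section 3.1 describes a study "in ~25 patients with advanced HCC". Sections 2.1 and 7.1 likewise say only advanced HCC.

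**The concern.** A response endpoint needs something that can respond. If a patient enters with no lesion measurable by mRECIST and cannot be scored as a complete or partial responder, that patient still occupies one of the 15 or 25 places and counts as a non-response whatever the drug does. With 25 patients, one such patient is 1/25 = 4% of the denominator. The risk is that an active drug is dropped, at the interim look or at the end.

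The second issue is who may enter. Criteria 3 and 4 sit in a list in which every item must be met, but a treatment-naive patient cannot have progressed on, or been intolerant to, first-line therapy. Sites may resolve this differently, or treatment-naive patients may be enrolled and then logged as eligibility deviations. The latter would bear on the per-protocol analysis in section 7.2, which leaves out patients with major protocol violations.

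The third issue is description. Section 1.3 names a line of therapy and an inflammatory type of HCC. The sections that set the objective, design and sample size name neither.

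**Working it through.** **Inputs**

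- From section 7.1: p0 = 0.05, p1 = 0.25, n1 = 15, stop at 0 responses, n = 25, success at 4 or more responses, one-sided error 0.05, power 0.90.
- From section 7.2.1: intention-to-treat denominator; no measurable lesion needed to be evaluable.
- Assumed: the share m of enrolled patients who cannot be scored as responders, taken as 4%, 10% and 20%. The documents give no figure.
- Assumed: response means complete or partial response. Section 2.1 lists all four mRECIST categories under ORR and does not say which count.

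**Step 1. Reproduce the stated design.** With X1 ~ Bin(15, p) and X2 ~ Bin(10, p), independent,

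P(success) = sum over x = 1, 2, 3 of P(X1 = x) × P(X2 ≥ 4 − x), plus P(X1 ≥ 4).

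At p = 0.25:

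| Stage 1 count | P(X1) | P(enough in stage 2) | Product |
|---|---|---|---|
| 1 | 0.0668 | 0.4744 | 0.0317 |
| 2 | 0.1559 | 0.7560 | 0.1179 |
| 3 | 0.2252 | 0.9437 | 0.2125 |
| 4 or more | 0.5387 | 1 | 0.5387 |
| Total | | | 0.9008 |

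The same sum at p = 0.05 gives 0.0336. The stated power is reproduced. The stated 0.05 is the ceiling used to choose the design; the attained error is 0.034. An exhaustive search confirms that 15 then 25 patients with these boundaries is the minimax design.

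**Step 2. Add patients who cannot respond.** If a share m of the intention-to-treat denominator cannot be scored as a responder, the response rate over all enrolled patients is p × (1 − m). Putting that into the same formula:

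| m | Rate if p = 0.25 | Power | Chance of stopping at 0/15 | Rate if p = 0.05 | Type I error |
|---|---|---|---|---|---|
| 0 | 0.250 | 0.901 | 0.013 | 0.050 | 0.034 |
| 4% (1 of 25) | 0.240 | 0.880 | 0.016 | 0.048 | 0.030 |
| 10% | 0.225 | 0.843 | 0.022 | 0.045 | 0.024 |
| 20% (5 of 25) | 0.200 | 0.762 | 0.035 | 0.040 | 0.016 |

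The chance of missing a drug with a 25% rate is 1 − 0.901 = 0.099 at m = 0, 1 − 0.880 = 0.120 at 4%, and 1 − 0.762 = 0.238 at 20%. Type I error falls throughout, so the loss is of power only.

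**Step 3. Criteria 3 and 4 under the combining rule.**

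| Patient | Criterion 3 | Criterion 4 read as a condition on treatment-naive patients | Eligible? |
|---|---|---|---|
| Previously treated, Child-Pugh A to B7 | can be met | does not apply | yes |
| Treatment-naive, Child-Pugh B7 | cannot be met | met | no |

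So the patients for whom criterion 4 was written are shut out by criterion 3. Criterion 2 writes out its alternatives with an explicit OR; nothing of the kind joins criteria 3 and 4. If they were meant as alternatives, the trial would take untreated patients, which does not fit the second-line aim in section 1.3. The text is unreconciled on either reading.

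**Step 4. Description of the population.** Inflammatory describes the study population in section 1.3. It has no definition or marker in sections 3.3.1 and 3.3.2 and does not describe the population in sections 2.1, 3.1 or 7.1.

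**The case against.** **Most patients will have a lesion anyway.** Three of the four diagnostic routes need a focal lesion of 1 cm or more with arterial hypervascularization, and everyone has a screening mRECIST assessment. This stands as a reason to expect a small share: at 1 patient in 25 the loss is 0.901 − 0.880 = 0.021. It does not close the gap. The fourth route carries no lesion requirement, the diagnostic routes say how HCC was established and not what the baseline scan shows, and criterion 3 patients have been treated since.

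**The power figures rest on what the documents leave open.** This also stands. The shares are assumed, the documents do not reproduce the mRECIST rules, and section 7.1 mixes ORR with clinical benefit. If stable disease counted as success, the calculation in step 2 would not apply.

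**Stronger readings that a reader might infer, and that the documents do not support:**

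- That nothing identifies second-line patients. Criterion 3 does so by requiring progression on, or intolerance to, first-line therapy.
- That criteria 3 and 4 together leave nobody eligible. Criterion 4 can be read as applying only to treatment-naive patients, and previously treated patients then still qualify.
- That treatment-naive patients are barred and are also pooled with treated patients under one 5% null. These are opposite readings. Under the literal rule none enters and there is no pooling; pooling arises only if the two criteria are alternatives.
- That the result could not be tied to the population the trial tests. The second-line and inflammatory wording stands in the rationale, whereas the objective, design and sample size refer to advanced HCC.
- That inflammation is ignored. Section 2.3 relates changes in pro-inflammatory cytokines to mRECIST response as an exploratory objective.

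The study flowchart is not shown in the text available, so it could not be checked for entry routes.

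**Conclusion.** The point holds in three parts of unequal weight.

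The missing measurable-lesion criterion is the main one. The sample size is correct as calculated, but its 90% power presumes that every enrolled patient can be scored as a responder, and eligibility does not secure that. The loss is modest at one patient (power 0.880) and material only if the share is large (0.762 at 5 of 25). It rests on the assumed shares and on response meaning complete or partial response. There is no inflation of type I error.

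The conflict between criteria 3 and 4 is real on the text and does not depend on any assumption about numbers. The documents show that the two criteria and section 1.3 must be reconciled; they do not show which way.

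The word inflammatory is a mismatch between one sentence of rationale and the rest of the protocol. It calls for alignment and is not evidence that the trial selects the wrong patients.

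These changes should be made; the design itself survives.

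**What to change.** 1. Add to section 3.3.1 an inclusion criterion requiring at least one lesion measurable by mRECIST on the baseline scan. The scan is already scheduled, so the change is one line of eligibility text. The cost is that a few patients with non-measurable disease are excluded.
2. Reconcile criteria 3 and 4 with each other and with the aim in section 1.3, stating plainly whether treatment-naive patients may enter. This point does not say which rule is right.
3. If both entry routes are kept, pre-specify a descriptive table of week-8 response by route (previously treated, treatment-naive). With 25 patients, 25 × 0.05 = 1.25 to 25 × 0.25 = 6.25 responders are expected across the two hypotheses, so the table can describe but not compare. It needs no new data.
4. Align the word inflammatory in section 1.3 with the population actually enrolled. This costs only wording.
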